3.4. Study Participants

3.4.1. Approaching study participants

Local research teams have established links with schools involved in the earlier assessment study and have secured interest for participation in the pilot and RCT. Student ambassadors (see Section 9) contributed to the development of study materials and both the assessment and intervention apps. Within participating schools, selected classes are invited to join the study. Parents are informed in advance and asked to provide consent (see Section 4.3). During school hours, local researchers and BootStRaP Ambassadors (teachers or students) introduce the study, answer questions, and obtain student assent. Participation is entirely voluntary, with no pressure from schools.

3.4.2. Sample size, basic assumptions

The pilot study and the RCT study are the second and the third in a series of three studies building upon each other, which will be conducted within the BootStRaP project. Therefore, considerations regarding sample size and power estimates include the prospect of interventions introduced in subsequent studies. As yet, there is little evidence of the effectiveness of this kind of intervention on PUI (specifically as measured by the PIUQ).

For the pilot study we assume $\alpha=0.05$, $1-\beta=0.8$, and a small effect size $d=0.3$, giving a required sample size $n=176$ per group. We assume 70% of randomised young people will complete follow-up. We also assume that 30% of children are high risk. To provide a cohort of 176 high risk children followed up requires a total sample of $n=838$ per group ($n=176/0.3/0.7$). The pilot study assumes 3 groups (random allocation to the Emotional regulation intervention, the Inhibitory control intervention, and a control groups). A 4th group of equivalent size to each study arm is required for validation of the algorithm developed in the machine learning phase; this group will be drawn at random from the sample allocated to each study arm. This giving a total sample size of $4*838= 3352$, or 373 per study site. All other analyses are secondary and will be evaluated using appropriate GLM models.

For the RCT, we assume $\alpha=0.05$, $1-\beta=0.8$, with cluster size=30 and effect size $d=0.3$, requiring $n=176$ per group. To allow for 70% completion, and 30% of children at risk, the total per group $N=838$. For the trial the sample size is $3*N=2514$ or 279 per study site.

4. Study Procedures

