Emotion regulation strategies			X	
Transfer of strategies			X	
Connecting emotion with thoughts (psychoeducation)				X
Connecting Emotion with thoughts (memory game)				X

Transfer to daily life	X>
Emergency plan	X
Inhibitory control intervention	
UUPS-P	X>
CHI-T	X
Impulsive Behaviour/consequences video	X
Challenge to observe behaviour	X
Skills for impulse control	X
Psychoeducation (text) connecting impulsivity with PUI	X>
Specific alternative behaviours for PUI	X>
Dealing with problems	X>
Transfer of strategies	X>
Emergency plan	X>

Additional Intervention tasks both intervention A and B

- Breath analyser
- Positive self-instructions

Note. # Assessed for 7 continuous days, -> denotes the period of continuous recording. + Continuous recording, > High PUI risk group only.

S-CIUS: Short-Compulsive Internet Use Scale

PRISM Internet, self-developed importance activity

RR & SER: Readiness and Self-efficacy Ruler

DBQ-I: Decision Balance Questionnaire

ERQ-CA: Emotion Regulation Questionnaire for Children and Adolescents

UPPS-P: Urgency – Premeditation - Perseverance - Sensation Seeking - Positive Urgency

CHI-T: Cambridge-Chicago Compulsivity Trait Scale

IUES: Internet Use Expectancies Scale

FoMO: Fear of Missing Out Scale

FoMO single: Fear of Missing Out single question

[figure not shown]

Figure 1. Flow diagram of Pilot study. For the control group, the division into high and low PUI risk will be for analysis purposes only. The two theory driven interventions (emotional regulation; inhibitory control) are delivered as high and low intensity versions, based on assessment of PUI risk at baseline. However, both low and high intensity forms of intervention are analysed collectively within each theoretical interventional model.

Table 3: Schedule of assessments for the optional extension to the pilot cohort (cohort 2). At week 18 of the pilot study, participants receive a push notification to re-confirm agreement to take part in the study extension. Assessments then take place at the indicated time-points.

Variable	Assessment time-point (months after entry to the extension period)																										
	1	2	3	4	5	6	7	8	9	10	11	12	13	14	15	16	17	18	19	20	21	22	23	24	25	26	27
PUI and clinical variables																											
S-CIUS	x	x	x	x	x	x	x	x	x	x	x	x	x	x	x	x	x	x	x	x	x	x	x	x	x	x	
PIUQ						x				x					x			x				x					
ISAAQ-10 Part A						x				x					x			x				x					
ISAAQ-10 Part B						x				x					x			x				x					

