Outcomes: The full list of outcome measure assessments including the period of mobile sensing is shown in table 1 and further details about each assessment and mobile sensing variable can be found in section 6.1.1. The primary main outcome measure assessment for both the pilot study and the RCT will be PUI severity as measured using the Problematic Internet Use Questionnaire in its short version (PIUQ-SF-9)(Demetrovics et al., 2008) Outcomes will be assessed digitally via a series of self-report questionnaires after sending out push-notifications for invitation as well as reminders in case of non-completion. Additional outcome data is collected via the Dragon Game app, which includes cognitive assessment tasks for affect regulation and inhibitory executive control. As a complementary modality for secondary outcome assessment, smartphone behaviour (data tracking) will also be measured

[figure not shown]

Figure 3. Flow diagram of RCT study. Allocation takes place twice; at week 0 all participants are randomised to either the tailored allocation arm or the random allocation arm or the control arm. At week 2 participants in the tailored allocation arm are allocated to the emotional regulation intervention or the inhibitory control intervention based on prediction of outcome algorithms developed in the Pilot Study. In the random allocation arm participants are randomised to either the emotional regulation arm or the inhibitory control arm. Regardless of the theoretical model of intervention (emotional regulation; Inhibitory control) all participants in either the tailored allocation arm or the randomised allocation arm will be analysed together as we are interested in the effect of the method of allocation on outcomes.

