6.3.3. Secondary analyses

Pilot Study

In the pilot study, secondary analyses will examine group differences, including at-risk versus no-risk participants, gender comparisons, and subtype comparisons among at-risk adolescents, based on PUI symptoms and burden. These analyses will employ multiple-hierarchical (moderated) regression models to explore interactions between predictor and moderator variables in predicting PUI symptoms and clinical outcomes (including burden) at T1.

Structural equation modelling (SEM), covering both manifest and latent variables, will assess relationships and interactions between PUI symptoms, clinical variables, and moderating/mediating factors (T0+3 assessment). The SEM will align with the Bootstrap logic model (Figure 4).

Randomised Control Trial

For the RCT, each factor (allocation method, intervention) will be analysed separately. The same analytical approach as the pilot study will be used, focusing on group differences (at-risk vs. no-risk, gender, subtypes of at-risk adolescents) through multiple-hierarchical regression analyses at T2.

SEM will also be applied to explore symptom interactions and moderating/mediating variables (T0+3 assessment), following the BOOTSTRAP logic model.

Missing data will be assessed for potential estimation bias. If data are missing at random (MAR), multiple imputation will be used. Where missingness is linked to specific demographic or psychological variables, alternative sensitivity analyses will be considered.

Additionally, a health economic analysis within the BootStRaP project will assess both the cost and burden of PUI among adolescents and evaluate the cost-effectiveness and cost-utility of the Emotional regulation intervention and Inhibitory control intervention. These analyses will focus on optimal intervention delivery using the developed risk algorithms.

The economic evaluation will be conducted from both mental health and societal perspectives, considering direct and indirect costs. From a mental health perspective, costs will include expenditures credited to the mental health care budget, aligning with the decision-maker's viewpoint. The societal perspective will encompass direct mental health care costs as well as indirect costs, such as productivity

losses and broader economic impacts. The analysis will incorporate discounting methods for the time horizon used, ensuring a comprehensive view of long-term costs and benefits.

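### The RCT's 80% power at d = 0.3 belongs to 176 high-risk completers per arm, but its three primary questions are not restricted to high-risk participants

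*Protocol*

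**What the plan says.** Section 3.4.2 takes alpha 0.05, 80% power and d = 0.3, "giving a required sample size $n=176$ per group". Two inflation factors follow: "We assume 70% of randomised young people will complete follow-up" and "We also assume that 30% of children are high risk". For the pilot the purpose is explicit: "To provide a cohort of 176 high risk children followed up requires a total sample of" 838 per group, that is 176/0.3/0.7. For the RCT the same section repeats d = 0.3 and 176 per group, cites a cluster size of 30, allows again for 70% completion and 30% at risk, and arrives at the same 838 per group and 2514 in total.

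Section 6.3.2 sets three RCT primary questions: active intervention versus control (2:1), tailored versus random allocation, and emotional regulation versus inhibitory control. It says these analyses need 3 × 838 = 2514. No question mentions risk status. Section 3.1.1 states that the whole adolescent population is included rather than subgroups.

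Risk status appears under section 6.3.3, Secondary analyses, where the RCT regressions are described as "focusing on group differences (at-risk vs. no-risk, gender, subtypes of at-risk adolescents") and placed at T2, whereas the primary endpoint is the post-intervention assessment (T1). For the pilot, the Figure 1 legend says that "both low and high intensity forms of intervention are analysed collectively within each theoretical interventional model".

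**The concern.** Dividing by 0.3 makes sense only if the comparison to be powered is between arms among high-risk completers. That comparison, at the primary endpoint, is not specified as primary anywhere in the protocol. The analyses that are primary use all participants, about 70% of them low risk, and carry no power statement of their own.

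Two things are at stake. First, a reader who takes 80% power at d = 0.3 as a property of the RCT's primary tests is misinformed in either direction: true power may be well below or well above 80%, depending on an effect in low-risk participants that the protocol does not give. Second, the document leaves room to argue after the fact about which population counts. A null pooled result could be set aside by pointing to the high-risk stratum as the one that was powered, or the reverse.

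Some dilution is plausible on the protocol's own description. Section 4.6 gives the additional elements only to participants at or above the S-CIUS cut-off of 9, and section 3.2 describes in-depth modules for higher-risk participants and general guidance for the others.

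**Working it through.** **Inputs (section 3.4.2):** alpha 0.05 (two-sided reproduces the plan's figure; one-sided gives 138 and does not), power 80%, d = 0.3, completion 70%, high-risk share 30%. **Allocation ratio:** section 6.3.2. **Planned recruitment:** 3,600 per cohort (Study Summary).

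**1. The plan's own figure.** The two-sample t-test at d = 0.3 needs 175.4, so 176 per group. Inflation: 176/0.3/0.7 = 838.1. Totals: 4 × 838 = 3352 (pilot) and 3 × 838 = 2514 (RCT). All reproduce. Power with 176 versus 176 is 80%.

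**2. What the pooled RCT analyses have.** Completers per arm: 838 × 0.7 = 586.6, about 587, of whom 0.3 × 586.6 ≈ 176 are high risk and about 411 low risk. Everything below is before any design effect; the protocol cites a cluster size of 30 but gives no intracluster correlation, and 176 is the unclustered figure.

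**3. Detectable effect at 80% power,** (1.96 + 0.8416) × √(1/n₁ + 1/n₂):
- Tailored versus random, 587 versus 587: 2.8016 × √(2/586.6) = 0.164.
- Active versus control, 2:1, about 1,173 versus 587: 2.8016 × √(1.5/586.6) = 0.142.
- Emotional regulation versus inhibitory control: the 1,173 active-arm completers divide according to the algorithm. If the tailored arm splits evenly, the comparison is 587 versus 587 and the figure is 0.164. If the algorithm sends the whole tailored arm to one intervention, it is 880 versus 293: 2.8016 × √(1/879.9 + 1/293.3) = 0.189.

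**4. Power when d = 0.3 holds in the high-risk stratum.** Pooled d = 0.3 × 0.3 + 0.7 × d_low. Power = Φ(d√(n/2) − 1.96) for 1:1 and Φ(d√(n/1.5) − 1.96) for 2:1, with n = 586.6. The low-risk effect is not in the protocol, so the first column is an assumption.

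| Low-risk d | Pooled d | Power 1:1 | Power 2:1 |
|---|---|---|---|
| 0 | 0.09 | 34% | 43% |
| 0.05 | 0.125 | 57% | 70% |
| 0.10 | 0.16 | 78% | 89% |
| 0.15 | 0.195 | 92% | 97% |
| 0.30 | 0.30 | 99.9% | >99.9% |

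Power falls below 80% only if the low-risk effect is under (0.1636 − 0.09)/0.7 ≈ 0.105 for 1:1, or (0.1417 − 0.09)/0.7 ≈ 0.074 for 2:1.

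**5. At planned recruitment.** 3,600/3 = 1,200 per arm; × 0.7 = 840 completers, of whom 252 are high risk. Detectable effects are 0.137 (1:1) and 0.118 (2:1). For low-risk effects of 0/0.05/0.10/0.15, power is 45/73/91/98% (1:1) or 57/84/97/>99% (2:1). The high-risk comparison at d = 0.3 has 92%. The mismatch is the same.

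**The case against.** The strongest reply is that sizing a study so that its smallest subgroup of interest is powered is a recognised conservative choice, and that it leaves 587/176 ≈ 3.3 times as many completers for the pooled test. Section 3.4.2 states d = 0.3 without limiting it to high-risk children, and if it holds generally the pooled comparisons are very well powered. This stands, and it rules out the reading that the RCT is underpowered. A reader might infer that from the lower rows of power, but those rest on an assumed low-risk effect. Nor does the protocol say that low-risk adolescents have little room to improve: risk is set on the S-CIUS, the study summary and section 3.3 name the PIUQ-SF-9 as primary outcome, and no score distribution is given.

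A reader might also extend the point to the pilot's primary analysis. Sections 2.1 and 6.3.2 make the pilot's primary question prediction of individual response, with effectiveness against control secondary. One sentence in 6.3.2 does call between-group comparison the focus of the primary analysis, but that is an inconsistency within the pilot text and not a basis for treating it as a whole-arm efficacy trial.

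The Figure 3 legend, under which "all participants in either the tailored allocation arm or the randomised allocation arm will be analysed together", might be taken as a statement about risk strata. Its opening words concern the two intervention models, so it shows pooling across interventions. The RCT case rests instead on the unrestricted primary questions and on the place of risk status in 6.3.3.

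Finally, one might conclude that the high-risk stratum should become primary. Section 3.1.1 speaks against that; it would change the question being asked.

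None of this supplies a power statement for the three RCT primary questions.

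**Conclusion.** The point holds for the RCT as a mismatch between the analysis that was sized and the analyses that are primary. The arithmetic in section 3.4.2 is correct, but its 80% power at d = 0.3 belongs to about 176 versus 176 high-risk completers, a comparison that is not primary. Section 6.3.2 nevertheless presents the resulting 2514 as the requirement of the primary analyses.

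Whether the pooled tests have more or less than 80% power cannot be settled from the protocol. The figures above assume the same SD in both strata and in the pooled sample, 70% completion in each stratum, and no clustering effect. For the pilot, the narrower statement is that the d = 0.3 calculation does not address its primary question, which is prediction.

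**What to change.** Keep the whole-sample comparisons primary, in line with section 3.1.1, and amend sections 3.4.2 and 6.3.2 as follows.

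- **RCT, primary questions.** State power or detectable effect for each question at its own ratio. At 838 per arm this is d ≈ 0.142 for active versus control and d ≈ 0.164 for tailored versus random. For emotional regulation versus inhibitory control, give a range over possible splits (about 0.164 to 0.189 by the calculation above), because the algorithm sets the split. If 3,600 is the intended size, use 0.118 and 0.137 for the first two. Say whether a design effect for the cited cluster size applies.
- **RCT, high-risk stratum.** Name the between-arm comparison in the baseline high-risk stratum, at the primary endpoint, as a pre-specified key secondary analysis, and attach the 176-per-arm, d = 0.3, 80% power statement to it.
- **Pilot.** Say that the d = 0.3 calculation supports the secondary effectiveness comparison in high-risk participants and not the primary prediction question.

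The cost is protocol wording and a less simple power statement. No extra participants or data are needed: the S-CIUS is collected at baseline.

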4.1. Study Setup

Ethics approvals for both the pilot study and RCT will be obtained from the nine collaborating academic institutions, either through joint or separate applications, depending on local requirements. The

University of Hertfordshire, as lead organisation, will provide standardised study documents (protocol, information sheets, consent/assent forms), which can be locally adapted. The study will be registered on ISRCTN.

BootStRaP Ambassadors (teachers and students) have been recruited at each site, and all participating centres will receive training in study procedures, including Good Clinical Practice (GCP) where needed. Governance is supported by a structured framework comprising a project office, steering committee, general assembly, and advisory boards (scientific, ethics, and impact). An independent reviewer will monitor study procedures and report to the project office and steering committee.

The BootstrApp Intervention app, which will manage questionnaires, mobile usage tracking, randomisation, and intervention delivery, is in development and expected to be ready by mid-2025. The Dragon Game app for BrainPAC tasks will also be completed within this timeframe. A secure data storage system, overseen by UZL, will store all assessment and intervention data.

A dedicated project website, www.internetandme.eu, provides information on this and related BootStRaP studies.

4.2. Recruitment

Each of the nine participating countries has established partnerships with local schools previously involved in the assessment app study, with agreements to continue in the BootStRaP project. At each school, at least one teacher and one student serve as BootStRaP Ambassadors, supporting engagement and retention throughout the pilot and RCT phases. Additional schools will be recruited if needed.

Where available, student organisations will also be engaged to support recruitment. Locally appropriate incentives (e.g. lotteries, competitions, or honoraria) will be used to encourage participation, tailored to each centre's context.

Local researchers and BootStRaP Ambassadors will introduce the study to students, explain its purpose, and demonstrate the BootstrApp Intervention app and Dragon Game app, which will be installed on students' smartphones. Students will have the opportunity to ask questions during these sessions.

Parents or guardians will receive an information pack and be invited to attend at least one session to learn more and ask questions. Participation requires parental consent and student assent. A holding page on the BootstrApp will require a unique code, provided during the information session, to confirm consent, assent, and school affiliation.

4.2.1. Study Campaign

During the assessment app study, national and local publicity campaigns were launched to raise awareness of the BootStRaP project. These included outreach through schools, community groups, local media, and digital platforms to engage students, parents, educators, and policymakers. As the project moves into Phase 2 (pilot and RCT), these efforts will be expanded with support from university press offices and international campaigns.

Delegates from candidate schools in each region will be invited to participate, helping to generate interest and enthusiasm. The research team will maintain regular communication with schools, offering detailed discussions of the study protocol to encourage involvement.

The BootStRaP consortium brings strong experience in media engagement, school collaboration, and adolescent recruitment, which will be leveraged to maximise recruitment, strengthen stakeholder engagement, and support the project's long-term impact across Europe.

4.3. Consent and Assent

For both studies, consent will be obtained prior to participation by parent or guardian for the student's participation and assent from the student. Where needed, the general consent procedure described below is adapted to local requirements.

Although in several countries some of the young people will be old enough to provide informed consent for themselves, as all children will be recruited through schools, we will ask for parental consent for all. Parents or guardians will be asked to provide consent (on behalf of their child), and children will be asked to provide assent to take part. Both parent or guardian consent and student assent will be collected either on paper or electronically outside of the app.

Those who consent to take part in Cohort 2 will also be invited to provide consent to the extension phase. Participants can still take part in Cohort 2 without consenting to take part in the extension phase. Those who consent to take part in both, will receive a push notification before the start of the extension asking them to re-confirm their agreement.

Parent or Guardian Consent

Parents or guardians will receive an information pack including instructions on how to provide consent. Depending on local circumstances, parents or guardians will also have the option to attend an information session if they want to find out more about the study. After being fully informed, they will be asked to give consent for their child's participation by completing an Informed Consent Form (ICF), either on paper or online (dependent on school policies and local requirements). A parent or guardian must give consent before their child can give their assent to take part. If they choose not to allow their child's participation, they can indicate this on the consent form.

Student Assent

Students who wish to participate will give their assent by agreeing to the statements in an assent form, on paper or online or by directly indicating their agreement to the researchers, depending on school policies and local requirements.

Downloading of the BootstrApp Intervention app

The study apps can be downloaded from a smartphone app store. Students who wish to take part will be asked to download the BootstrApp and Dragon Game App to their smartphone, with help from a parent, carer or researcher where needed.

Students can choose their preferred language on the BootstrApp. A holding page will then appear, stopping them from proceeding until consent and assent has been verified by a research team member.

Student Session

Students within the designated age range will be invited to attend an information session hosted by the research team and, possibly, their school ambassadors.

The research team will verify that both the parent or guardian's Informed Consent Form (ICF) and the student's assent has been provided. Once both have been confirmed, a unique code will be assigned to the form(s), and the student will be asked to enter this code into the BootstrApp. Once this code is entered, the student is officially enrolled and will begin the two-week assessment phase. The unique codes will be automatically generated before recruitment begins by the app development team and will consist of 8 alphanumeric characters.

Depending on local circumstances, the above activities may not all take place during a single information session but may be arranged separately.

The unique code ensures that the student's assent can be linked to their parent's authorisation if needed, such as in cases of premature withdrawal, and confirms that parental or guardian consent has been obtained. This code also identifies the time zone to send push notifications at the correct times and the school. For students whose parents have opted out, it will be clearly communicated that they will not be able to participate.

